#### **5.3.1 Imaging**

Screening imaging must be taken within 180 calendar days from the planned procedure date. Screening imaging to characterize the IA will consist of angiography.

#### **5.3.2 Antiplatelet agents**

The subject will be tested for antiplatelet response (using VerifyNow (Accumetrics) and the appropriate dose of antiplatelet agents will be given before Pipeline™ device treatment as defined below.

- **Aspirin:** At least 81 mg daily for a minimum of 7 days
- **Clopidogrel:** At least 75 mg daily for a minimum of 7 days

A loading dose option will not be permitted in the study. Subjects resistant to Clopidogrel will not be included in the study.

### **5.4 Procedure**

Subjects must undergo the device placement procedure within 60 calendar days of completion of all baseline assessment tests and procedures. The status of the target IA may change between the screening evaluation and the procedure that may change the risk profile of the study procedure.

Therefore, a pre-treatment (baseline) angiogram will be required before the procedure to confirm that the study procedure can be safely carried out and to collect precise images for the core laboratory. If in the unlikely event that the subject is deemed to be ineligible, the subject will not require any study follow-up.

Each subject will undergo a neurologic examination and assessment using NIHSS. The subject will be tested for antiplatelet response (e.g. using VerifyNow (Accumetrics)). Periprocedural heparin per institutional protocol is required. Prior to inserting the study device, the activated clotting time (ACT) should be checked and adjusted as clinically appropriate. Further ACTs will be checked per standard practice.

The physician will place and deploy the appropriate number of Pipeline™ device braids at the target site to treat the IA.

Post-treatment, the investigator will assess device occlusion, placement and overall status of the aneurysm. Angiograms in the anteroposterior (AP), lateral, and working positions will be obtained. The Investigator will take necessary steps to ensure that pre- and post-placement angiograms are performed using similar views, magnifications, and contrast amount to ensure valid “before/after” comparisons. However, these angiographic details will not be collected in case report forms (CRFs). The Investigator will submit procedural angiograms to the imaging core laboratory. The Investigator will ensure that subject identifiers are removed from all submitted images. Image files/CDs should be labeled with the subject’s study ID number.

Medications appropriate for general anesthesia will be administered using standard hospital practice. Platelet inhibition and aggregations status pre- and post-surgical intervention, including antiplatelet antibodies will be evaluated. All medication use during surgery and immediately post-procedure will be documented. Radiation exposure will be recorded as absorbed radiation dose and cumulative fluoroscopy time will be recorded.

At the investigator’s discretion, the target IA may be retreated at any time during the study. In the event that the target IA is not treated with the Pipeline™ device at the initial scheduled procedure, the subject may be brought in later to undergo the Pipeline™ device placement procedure. In such situations, the date that the subject receives the Pipeline™ device implant will be considered Day 0. Data will be collected for all initial and retreatment procedures.

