### Statistical Analysis:

With the general exception of the tests comparing the response to an *a priori* threshold, all statistical tests will be 2-sided, performed at the 5% significance level. *Baseline* is defined as the last observation recorded prior to the study procedure.

The primary safety endpoint is the incidence of major stroke in the territory supplied by the treated artery or neurological death recorded within 1 year of the study procedure. The incidence will be summarized using counts and percentages; the 1-sided upper bound of the 97.5% confidence limit for the incidence will be evaluated relative to the *a priori* threshold of 15%. The primary effectiveness endpoint is the incidence of complete aneurysm occlusion at 1 year post-procedure. Results will be summarized using counts and percentages; the 1-sided lower bound of the 97.5% confidence limit for the incidence will be evaluated relative to the *a priori* threshold of 50%.

To ensure the study is not under-powered, the primary endpoint will be monitored by the DSMB. After 50 subjects have been treated and followed for a minimum of 6 months post-procedure, an interim assessment will be performed. It is understood that monitoring off an earlier time point does not correspond with the primary endpoint. However, to derive an initial signal to ensure that the observed incidence is commensurate with the planning estimates, this time point should conservatively represent approximately 80% of events at 1 year. Details of the procedure will be described in the DSMB Charter.

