- Non-index procedure related: This includes AEs attributable to any device(s) used at procedures other than day 0, such as access devices, delivery microcatheters, non-ionic contrast, guidewires, or any other adjunctive, approved/cleared device for treatment of intracranial aneurysms. This may include commercially available Pipeline™ devices used in procedures other than at Day 0 or those used on non-target lesions.
- DAPT-related: Event is clearly attributable to dual antiplatelet therapy (DAPT) with no temporal relationship to the device, treatment, or medical history.
- Unknown: Event relationship cannot be attributed to any of the above categories and remains undetermined.

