## **21 DEFINITIONS**

TERM	DEFINITION
Adverse Event (AE)	Any untoward medical occurrence, unintended disease or injury, or untoward clinical signs (including abnormal laboratory findings) in subjects, users or other persons, whether or not related to the investigational medical device. (ISO 14155:2011 3.2)
Adverse Device Effect (ADE)	An adverse event related to the use of an investigational medical device. (ISO 14155:2011 3.1)
Aneurysm Occlusion	According to the scale of Roy: Complete = Complete occlusion, no flow of contrast seen in the aneurysm sac Residual Neck = Partial occlusion, some flow or eddying flow in the aneurysm sac Residual Aneurysm = Incomplete occlusion, apparent flow in the aneurysm sac
Device Migration	Movement of one or more Pipeline™ devices of more than 5 mm in its parent artery location in comparison to the post-placement angiogram
Device-related Adverse Event	Event has a strong temporal relationship to the study device, and alternative etiology is less likely.
Enrolled Ineligible	Enrolled subject who did not meet study eligibility criteria.
Full Analysis Set Population (FAS)	All enrolled subjects including only those in whom the Pipeline™ device was implanted.

TERM	DEFINITION
NIH Stroke Scale (NIHSS)	Tool to quantify neurological impairment caused by stroke 0 No Stroke Symptoms 1-4 Minor Stroke 5-15 Moderate Stroke 16-20 Moderate to Severe Stroke 21-42 Severe Stroke
Procedure	The primary study procedure involving the placement of the Pipeline™ device at Day 0.
Intention to Treat Population (ITT)	All enrolled subjects in whom deployment of the Pipeline™ device was attempted. It is possible that the Pipeline™ device may not reach the target site and the operator would not attempt to deploy it, in the rare event that happens, that subject will not be considered part of the ITT population.
Medium Intracranial Aneurysm	7-12 mm

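### When a deployment attempt fails and the subject is implanted later, Day 0 moves to the implant date, and no rule counts a major stroke from the first attempt in the safety endpoints

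*Combined protocol and SAP*

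**What the plan says.** Section 5.4 provides that if "the target IA is not treated with the Pipeline™ device at the initial scheduled procedure, the subject may be brought in later" for placement, and in that case "the date that the subject receives the Pipeline™ device implant will be considered Day 0". It adds: "Data will be collected for all initial and retreatment procedures".

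The rest of the plan hangs on Day 0:

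- **Procedure.** Section 21 defines it as "The primary study procedure involving the placement of the Pipeline™ device at Day 0".
- **Safety clock.** The synopsis counts the primary safety endpoint when "recorded within 1 year of the study procedure". Section 3.2 counts the procedural safety endpoint at 30 days post-procedure.
- **Baseline.** The synopsis says that it "is defined as the last observation recorded prior to the study procedure". Section 5.4 requires an NIHSS assessment at the procedure visit.
- **Relatedness.** Section 6.1 ties the procedure-related category to Day 0 and limits the investigational device to the one used on Day 0. An event from a Pipeline device used at any other procedure goes to the non-index category: "This includes AEs attributable to any device(s) used at procedures other than day 0".
- **Populations.** Under Section 9.3, ITT requires an attempted deployment and FAS requires an implant. Section 9.4 names both for primary safety.

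**The concern.** Follow a subject in whom deployment is attempted without success, who has a major stroke, and who is implanted at a second session. The stroke comes before Day 0 and therefore before the procedure as Section 21 defines it. Read as written, it is outside the 1-year and 30-day windows. If the device caused it, Section 6.1 files it as non-index, so it is also missing from the 1-year device-related neurologic rate in Section 9.9.

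Choosing between ITT and FAS does not repair this. Once implanted, the subject belongs to both sets; the event is lost by its date, not by the population.

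The NIHSS reference is exposed too. Section 3.1 defines major stroke by a rise of at least 4 points without naming the reference value. If the general baseline definition fills that gap, the last NIHSS before the implant, taken after the event, could become the reference.

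This is a single-arm test against a fixed 15% goal, so no control arm offsets an omitted event. Because the reset needs a later implant and can only remove events, any error runs in the device's favour.

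**Working it through.** **1. Reproduce the plan's own figure.** Inputs from Sections 9.2 and 9.4: threshold 15%, 1-sided 97.5% Clopper-Pearson upper bound, planning rates of 5% to 9%. The bound for x events in n subjects is the 0.975 quantile of Beta(x + 1, n − x). Taking the smallest n with a bound below 0.15, and leaving x = rate × n as a fraction, gives 52, 63, 80, 104 and 141. All five rows of Table 7 are matched.

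**2. Find the decision boundary at n = 141, in whole events.**

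| Events | Rate | Upper bound | Below 15%? |
|---|---|---|---|
| 8 | 5.7% | 10.87% | yes |
| 9 | 6.4% | 11.77% | yes |
| 12 | 8.5% | 14.39% | yes |
| 13 | 9.2% | 15.25% | no |
| 14 | 9.9% | 16.10% | no |

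The planning rate behind N = 141 gives 0.09 × 141 = 12.69 events, which lies between the last pass and the first fail. There, one uncounted event decides the result. Near 8 events, adding one changes nothing.

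**3. Size the average effect.** The documents give neither the share of subjects brought back after a failed attempt (f) nor the risk of a qualifying event at that attempt (r). Assumed ranges: f = 1% to 5%, r = 2% to 10%.

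- Expected omitted events = 141 × f × r. Low: 141 × 0.01 × 0.02 = 0.03. High: 141 × 0.05 × 0.10 = 0.71.
- If the true rate is 15%, the counted rate is 0.15 − f × r, that is 0.1498 at the low end and 0.1450 at the high end.
- The false-pass probability is P(X ≤ 12) for a binomial with n = 141 and the counted rate. With every event counted it is 1.57%. Over the assumed ranges it is 1.60% to 2.31%. The nominal level is 2.5%.

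**4. Extreme case for comparison.** If exactly one event were omitted in every trial, the false-pass probability would be P(X ≤ 13) at 15% = 3.0%. With two it would be P(X ≤ 14) = 5.3%. These show how sensitive the boundary is; they are not expected values.

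**The case against.** The strongest reply is that the path is narrow and the events stay visible.

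- **Trigger.** Section 5.4 speaks of an aneurysm not treated at the first procedure, which includes postponement, and never mentions a failed attempt. This stands, but the wording does not exclude one, and Sections 6 and 9.3 both foresee surgery or an attempt that ends without an implant.
- **Selection.** The subject must have a qualifying stroke, survive and still be implanted. Exclusion 2 bars subarachnoid hemorrhage in the past 30 days, exclusion 7 lets the investigator exclude for recent clinical worsening, and Section 5.3 allows no waivers. This stands, and it makes the path rarer. It does not close it, because exclusion 7 is a judgement and both exclusions look back only 30 days. A death at the first attempt cannot enter this path at all; it belongs to the separate ITT/FAS conflict in Section 9.4.
- **Recording.** A reader might infer that these events disappear. They do not. Section 6 collects adverse events from consent, Section 9.11 treats events after enrollment as treatment-emergent, and the 30-day limit in Section 6 concerns only subjects never implanted.
- **Adjudication.** Section 8.1 sends sudden deterioration of at least 3 NIHSS points to the clinical events committee. But the committee works to the stated endpoint definitions, and Sections 9.11.7 and 9.11.8 bind it to Section 6.1 for relatedness. Review is not a rule for counting.

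Three further inferences go beyond the documents:

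- The 3.0% and 5.3% figures do not show that the test exceeds its nominal level, since they omit one or two events in every trial.
- The 1 braid in 47 not placed in the PITA study (Section 1.2.3) is a per-braid figure and does not say how many subjects would be brought back.
- A shifted mRS baseline does not alter the 1-year mRS result, which Section 9.9 dichotomises as an absolute score; the schedule lists no mRS at the procedure visit.

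**Conclusion.** The gap is real and follows from the stated definitions. For a subject with an attempted deployment before a later implant, a major stroke from the first attempt precedes both safety windows, and a device event there is classed as non-index. The effect on the NIHSS reference is a possibility rather than a stated rule, because Section 3.1 is silent on the reference value.

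The expected effect is small: under one omitted event across the assumed ranges, with the false-pass probability below 2.5%. Those ranges are assumptions. The case for correction rests on three other facts: the error has one direction, a single event separates pass from fail at 12 versus 13 of 141, and N = 141 was set for a rate at that boundary. The documents do not support a claim that the safety test is invalid or that harm is hidden from the safety tables.

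**What to change.** Amend Sections 5.4, 6.1, 9.4 and 21 for subjects with an attempted deployment before the procedure at which they are implanted:

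1. Count primary safety events from the first attempted deployment through 1 year after the implant, and 30-day procedural events from the first attempt through 30 days after the implant. Both ends must be stated. A window that starts at the first attempt and lasts only one year would drop late post-implant events.
2. Classify events from any such attempt as device- or procedure-related on their merits.
3. Name the last NIHSS before the first attempt as the reference for the major stroke criterion.
4. Use attempted deployment as the trigger, as in the ITT definition in Section 9.3.
5. Keep the implant date as Day 0 for the visit schedule and the 1-year angiogram.

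The cost is definition wording. No treatment or visit changes, and the data are already collected. The safety rate may come out slightly less favourable, and the period at risk is slightly longer for these few subjects. The rule should be settled before outcomes are known.

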## **5.5 Post-placement Antiplatelet Agents**

The subject should be tested for antiplatelet response per standard of care, and the appropriate dose of antiplatelet agents will be given after the Pipeline™ device placement procedure as defined below.

- **Aspirin:** At least 81 mg daily for a minimum of 6 months
- **Clopidogrel:** At least 75 mg daily for a minimum of 3 months

Medications could be continued beyond above regimen if medically indicated.

## **5.6 Discharge Exam**

Each subject will undergo a neurologic examination and assessment using the mRS and NIHSS. The Investigator will also document all medications currently being taken and adverse events. The subject may undergo platelet function testing as per standard patient care.

## **5.7 Follow-up Evaluations**

Subjects will undergo follow-up at a location designated by the research staff at 30 days, 180 days, 1 year, 2 years, and 3 years post-procedure.

### **5.7.1 30-Day**

At this visit, the subject will undergo a neurologic examination and assessment using the mRS and NIHSS. The Investigator will also document all medications currently being taken and assess adverse events.

### **5.7.2 180-Day**

At this visit, the subject will undergo a neurologic examination and assessment using the mRS and NIHSS. The Investigator will also document all medications currently being taken and adverse events. If the subject undergoes angiography of the target IA as standard care, the angiogram will be sent to the Core Laboratory for analysis. In addition, any axial imaging done in place of angiography may be collected and sent to the Core Laboratory for analysis.

### **5.7.3 1-Year**

At this visit, the subject will undergo a neurologic examination and assessment using the mRS and NIHSS. The Investigator will also document all medications currently being taken and adverse events. The subject will undergo angiography of the target IA. If available, imaging should include rotational angiography with 3D reconstruction. Imaging will be sent to the Core Laboratory for analysis.

### **5.7.4 2-Year**

At this visit, the subject will undergo a neurologic examination and assessment using the mRS and NIHSS. The Investigator will also document all medications currently being taken and adverse events. The subject may undergo angiography of the target IA if the aneurysm was not occluded at 1 year. If applicable, imaging will be sent to the Core Laboratory for analysis. In addition, any axial imaging done in place of angiography may be collected and sent to the Core Laboratory for analysis.

### **5.7.5 3-Year**

At this visit, the subject will undergo a neurologic examination and assessment using the mRS and NIHSS. The Investigator will also document all medications currently being taken and adverse events. The subject may undergo angiography of the target IA if the aneurysm was not occluded at 2 years. If applicable, imaging will be sent to the Core Laboratory for analysis. In addition, any

axial imaging done in place of angiography may be collected and sent to the Core Laboratory for analysis. This visit is the final study visit.

### 5.7.6 Unscheduled Visits

Any visit by the subject to the Investigator related to the target IA treated or a potentially associated adverse event should include a neurologic examination using NIHSS. The Investigator should document the review of the adverse event status and all medications taken by the subject.

## 5.8 Schedule of Assessments

An overview of the assessments to be performed at each follow-up interval along with the required timing is provided in **Table 5**. Visits occurring outside of the specified date range will be considered protocol deviations.

Visits		Screening and Baseline	Device placement		Follow-up					
Assessments	Time (Windows)	Pre-procedure (-60days)	Procedure	Discharge exam	30-day	180-day	1-year	2-year	3-year	Unscheduled
Assess Inclusion / Exclusion		◆								
Demographics and Medical History		◆								
Blood Labs		◆ 	◆ 	○ 						
Medications		◆	◆	◆	◆	◆	◆	◆	◆	◆
Modified Rankin Scale score		◆		◆	◆	◆	◆	◆	◆	
Imaging 	(180 days)	◆ 			○ 	◆	◆ 	◆ 	◆ 	
NIH Stroke Scale		◆	◆	◆	◆	◆	◆	◆	◆	◆
Pipeline™ Placement			◆							
Assess Adverse Events		◆	◆	◆	◆	◆	◆	◆	◆	

1 Includes CBC, HCT, platelet count, platelet function testing as per standard patient care, serum creatinine, and pregnancy test, if applicable

2 Includes platelet count and platelet function testing

3 If platelet function testing is performed as standard patient care the results should be recorded.

4 Includes angiograms in the anteroposterior, lateral and working positions for analysis by a core laboratory.

5 Includes a pre-treatment and post-treatment angiogram

6 If an angiogram is performed as standard patient care it should be sent to the core laboratory for analysis.

7 If aneurysm is completely occluded at 1 year, angiography is optional at subsequent follow-up visits. Otherwise if aneurysm is not occluded at 1 year, angiography must be performed thereafter until the aneurysm is completely occluded or the subject has completed the study.

Any angiograms performed at other time points should be sent to the core laboratory for analysis.

## 5.9 New Information

Study subjects will be informed of new information that becomes available during the course of this study by their treating physician. Subjects will be notified, at a minimum, in accordance with the IRB/EC's procedure for providing updated information to clinical study subjects.

## 5.10 Study Exit

Upon completion of the specified study follow-up the subject will be exempt from further data collection. The subject will be seen by the treating physician according to standard care following intracranial aneurysm treatment.

## **5.11 Termination of Subject Participation**

Subjects may withdraw from the study at any time without penalty or loss of medical care, or they may be withdrawn at any time at the discretion of the PI or Sponsor for safety or administrative reasons.

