### **5.11.2 Subject Discontinuation by Investigator**

An Investigator may discontinue a subject from the study, with or without the subject's consent, for any reason that may, in the Investigator's opinion, negatively affect the well-being of the subject. If a subject is withdrawn from the study, the Investigator will promptly inform the subject and Sponsor.

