### **5.11.3 Lost to Follow-up**

A subject will be considered lost to follow-up if the subject cannot be reached after three (3) attempts to contact the subject for a follow-up visit. The site must document a minimum of three (3) attempts, and the final documented attempt should be made via registered letter.

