### **5.12.2 Study Discontinuation by Sponsor**

The Sponsor may choose to discontinue the study should the Sponsor discover additional information during the study that may cause harm to subject safety.

If the study is terminated prematurely or suspended, the Sponsor will promptly inform all clinical Investigators of the termination or suspension and the reason(s) for this. The IRB/EC will also be informed, either by the Sponsor or Investigator if a local IRB/EC is utilized, promptly and provided with the reason(s) for the termination. If applicable, regulatory authorities will be informed. Enrolled subjects will be asked to complete all remaining study visits and the subject will then be seen by the treating physician according to standard care following intracranial aneurysm treatment.

Any investigator who is discovered during monitoring to have not reported neurologic adverse events may be terminated from the study at the discretion of the Sponsor

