## **6 ADVERSE EVENTS**

The following adverse events will be collected during the course of the study on the eCRFs.

- All Adverse Events (AE) with an underlying neurological cause (Neurological Adverse Events)
- All Device Related Adverse Events
- All Procedure Related Adverse Events
- All Serious Adverse Events (SAE's)

Adverse event status will be evaluated throughout the study. These will include new events occurring after the point of consent in the study until a subject exits the study. Subjects who are enrolled, underwent surgery to implant to study device but did not have the Pipeline™ device implanted for any reason will be followed for 30 days and relevant safety events will be collected. Investigators must obtain all information available to determine the causality and outcome of the AE and to assess whether it meets the criteria for classification as a serious and/or unexpected event requiring notification to the Sponsor, regulatory agency, and as applicable, IRB/EC, within the specified reporting timeframe. AEs will be categorized using the definitions in **Section 6.1**.

All study AEs, as well as the treatment and follow-up required, should be documented in the subject's medical records and in the eCRF. All study AEs will be followed by the Investigator until resolution or until the end of the 3-year follow-up. A list of potential anticipated adverse events is provided in **Section 10.2**.

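### Implanted subjects can be taken out of the study, or classed as lost after three failed contacts, with no stated duty to look for new strokes or deaths afterwards, so the 1-year safety rate can be understated

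*Combined protocol and SAP*

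**What the plan says.** Three rules in Section 5.11 can end a subject's participation without the subject asking to leave.

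- **Section 5.11 (opening text):** besides withdrawing themselves, subjects are told that "they may be withdrawn at any time at the discretion of the PI or Sponsor for safety or administrative reasons".
- **Section 5.11.2:** an investigator "may discontinue a subject from the study, with or without the subject's consent", where in the investigator's opinion the reason bears on the subject's well-being.
- **Section 5.11.3:** a subject is classed as lost "if the subject cannot be reached after three (3) attempts to contact the subject for a follow-up visit". Three is the documented minimum, and "the final documented attempt should be made via registered letter".

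None of the three separates subjects before implant from subjects after it. None says whether events or vital status are still collected afterwards, or whether contact is tried again when the next visit falls due.

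Section 6 has two relevant rules. New events are collected "until a subject exits the study". Adverse events already recorded are followed to resolution or to the end of the 3-year follow-up.

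Section 5.12.2 deals with the sponsor stopping the whole study, and there the plan does provide for continued observation: "Enrolled subjects will be asked to complete all remaining study visits". Section 5.11 has no counterpart for a single subject.

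On analysis, Section 9.4 counts subjects who do not complete the 1-year period and have no recorded event as event-free. Its only safety sensitivity analysis censors withdrawals. Section 9.1 likewise does not treat a missed 1-year visit as a safety failure unless stroke or death is known.

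**The concern.** The study treatment is an implant placed on Day 0. Taking a subject out of the study later does not undo it; what stops is the planned search for new events. The stated grounds for removal include safety and well-being, which are plausibly related to the risk of stroke or neurological death. A subject who cannot be reached may also be one who has become ill.

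If such a subject has a major stroke or dies of a neurological cause after exit but within the year, the plan has no procedure that would reliably find it, and the primary analysis enters the subject as event-free. Censoring the subject instead does not help, because censoring assumes that those who leave have the same later risk as those who stay. The primary safety conclusion, that the 1-year rate is below 15%, could then be reached on an incomplete count.

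**Working it through.** **Inputs from the documents.** Exact Clopper-Pearson limit, one-sided 97.5%, threshold 15% (Sections 9.2 and 9.4). N = 141 (Section 9.2). About 80% of 1-year events are assumed to have occurred by 6 months (Section 9.6).

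**Input not in the documents.** The rate of exit after implant. The only allowance is about 30% screen failure before treatment (Section 4.1). Every exit scenario below is therefore an assumption.

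**Step 1. Reproduce the plan's sample size.** With x events in n, the upper limit is U(x, n) = the 97.5th percentile of Beta(x + 1, n − x). The smallest n with U(n·p, n) < 0.15, allowing n·p to be fractional, is:

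| Observed rate p | n found | n in Table 7 |
|---|---|---|
| 5% | 52 | 52 |
| 6% | 63 | 63 |
| 7% | 80 | 80 |
| 8% | 104 | 104 |
| 9% | 141 | 141 |

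All five rows agree.

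**Step 2. Find the pass rule at n = 141.** U(12, 141) = 14.39%, a pass. U(13, 141) = 15.25%, a fail. The test passes with 12 events or fewer, so one unseen event can turn a fail into a pass.

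**Step 3. Compare counting as event-free with leaving out.** Suppose 15 subjects truly have an event: 15/141 = 10.6%, U = 16.94%, a fail. Suppose 3 of the 15 leave before the event is recorded.

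- Counted as event-free: 12/141, U = 14.39%, a pass.
- Left out of the denominator, as in the extreme of censoring at the start: 12/(141 − 3) = 12/138, U = 14.70%, a pass.

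The choice of 3 is illustrative. The point is that neither treatment of the exits restores the failing result.

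**Step 4. False-pass chance at a true rate of 15%.** This is P(X ≤ 12) for X ~ Binomial(141, q), where q is the rate that gets recorded.

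| Assumption about exits | q | P(pass) |
|---|---|---|
| Full follow-up | 15% | 1.6% |
| 10% leave at 6 months, unrelated to outcome | 15% × (1 − 0.10 × 0.20) = 14.7% | 2.0% |
| 10% of events missed | 15% × 0.90 = 13.5% | 4.7% |
| 20% of events missed | 15% × 0.80 = 12.0% | 12.3% |

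In the second row, 0.20 is the share of events expected after 6 months, that is 1 − 0.80.

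The third and fourth rows can be put in terms of subjects. If 30% of those who leave have an unseen event, 5% leaving gives 15% − 5% × 30% = 13.5%, and 10% leaving gives 15% − 10% × 30% = 12.0%. Those are the same recorded rates.

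**The case against.** The case on the other side has real substance.

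**Partial safeguards exist.** Recorded events are followed to resolution or 3 years (Section 6). A known stroke or death counts even if the 1-year visit is missed (Section 9.1). Source documents are requested for deaths (Section 6.2). Investigators who fail to report neurologic events may be removed (Section 5.12.2). Site physicians commit to pursuing the details of safety outcomes (Section 17.2). Withdrawals are tabulated with reasons (Section 9.10). This stands, and it narrows the gap to new events after exit. A reader might infer that all safety follow-up ends at removal; Section 6 does not support that for events already recorded.

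**Consent.** A reader might infer that the sponsor may remove a subject for administrative reasons without consent. The documents do not say so. The wording on consent is in Section 5.11.2 only, for the investigator, on well-being grounds.

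**Loss to follow-up.** A reader might infer that three failed contacts at, say, the 30-day visit cancel all later visits. Section 5.11.3 does not say this. It sets a minimum effort and a classification, and is silent on later contact. The defect is the absence of a duty to try again.

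**Analysis.** It would be too strong to say that analysis can do nothing. A worst-case or tipping-point analysis, which Section 9.5 already plans for effectiveness, would bound the bias in safety. It would not recover the missing outcomes, and none is planned for safety.

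**Size.** Nothing in the documents shows that discretionary removal will be frequent or related to outcome, and exit unrelated to outcome does little. This also stands, and is why the figures are given as a range.

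**Conclusion.** The point holds as a gap in follow-up after exit. The plan allows an implanted subject to leave by investigator or sponsor decision, or to be classed as lost, with no stated duty to ascertain later strokes or deaths, and then counts that subject as event-free for primary safety. The bias favours the device whenever exit is related to a worse prognosis.

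The margin is one event at n = 141. The false-pass chance at a true 15% rate is 1.6% with full follow-up, about 2.0% with 10% exit at 6 months unrelated to outcome, and 4.7% to 12.3% if 10% to 20% of events go unseen. These figures rest on N = 141, the exact one-sided 97.5% limit, the plan's assumption on event timing for the 2.0% figure, and assumed loss rates for the rest. The documents support saying that bias can occur. They do not support saying that it will, or that the subjects doing worst will be the ones removed. It is a cheap improvement worth making.

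**What to change.** **Sections 5.11 and 5.11.2.** State that, once deployment has been attempted, withdrawal by the investigator or sponsor ends protocol-specific procedures only. Collection of new stroke and death events and of vital status continues by visit, telephone or record review through 1 year, and on to 3 years, unless the subject withdraws consent.

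**Administrative reasons.** Keep this ground. Site termination (Section 5.12) and discontinuation at a center by the IRB/EC (Section 5.12.1) are foreseen and need it. Apply the same event and vital-status follow-up to these exits where permitted.

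**Section 5.11.3.** Treat three failed contacts as a missed visit. Repeat contact in each later window, including 1 year. Declare loss to follow-up only after the last window, with a vital-status check through the treating physician or records.

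**Cost.** Protocol wording, matching consent-form text, and a few calls or record checks per affected subject. The subject's own right to withdraw is unchanged, and so are the sample size and the test.
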